- Study using stored specimens/tissue
- Study using stored medical records
- Others.....

A.7 Is study single center or multicenter

- Single center
- Multicenter (within Nepal)
Please specify the study sites
- Multicenter (International)
Please specify the study sites

Note: NHRC Approval is compulsory for Ph. D/ International Study/ International Collaboration/ Multicenter & Clinical Trial Study.

A.8 Summary of the proposed research protocol (within 200 words)

Cholangiocarcinoma (CCA) or a bile duct cancer is regarded as the second most frequent type of primary liver cancer which is diagnosed in the late decades of life with fatal outcomes. Its risk factors include primary sclerosing cholangitis, hepatitis, smoking, alcohol, obesity, inflammatory bowel disease, cirrhosis, etc. As it is a fatal disease with late diagnosis, knowing the risk factors and its occurrence rate will be helpful to design interventions based on the evidence. It is also important for the early treatment and increased survival rate of patients. It is a quantitative observational type of study. The objective of this study is to collect the clinico-demographic profile of the patients with cholangiocarcinoma undergoing Endoscopic Retrograde Cholangiopancreatography (ERCP) in Dhulikhel Hospital. Self- structured Questionnaire will be used as a research tool for data collection based on literature review. This kind of research is crucial to widen the knowledge in prevention of the morbidity and mortality due to cholangiocarcinoma. Dhulikhel Hospital is a pioneer tertiary care center in Nepal for ERCP, where cases are from different parts of Nepal and their medical records will be reviewed to generate the

evidence of the clinico-demographic profile of the patient with cholangiocarcinoma undergoing ERCP.

A.9 Source of Funding/Sponsor

Non Funded

A.11 Declaration of Co-I

None

B. DETAIL OF THE STUDY

B.1. Background:

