Accounting for about 2% of all malignancies, CCA is considered as a rare malignancy.⁹ It rarely occurs before the fourth decade of life with a wide variation of incidence rates in different geographical regions that reflect the distribution of risk factors, both environmental and genetic.^{9,10} Hence it is known as the disease with late diagnosis and fatal outcome.¹¹ This form of cancer is prevalent in males compared to females and it is found to affect people in their fifth to seventh decade of life.¹¹ According to the American Cancer Society (2023), about 41,420 cases of liver and intra hepatic cancer are estimated including both sexes among which 29,380 deaths are reckoned.¹² CCA is regarded as the second most frequent type of primary liver cancer.¹³ Risk factors related to CCA may vary within different geographical variations.¹⁴ In case of hepatobiliary cancers, CCA accounts for about 20% of death whereas it constitutes 13% of total cancer mortality.¹⁵ As it is not more frequently diagnosed worldwide, it is also regarded as an orphan cancer.¹⁶

The treatment choice of CCA either surgical or radiological, is dependent on different factors such as anatomical position, lymph node and vascular invasion, metastatic condition, etc.^{13,16} In case of chemotherapy, combination of gemcitabine and cisplatin has been considered as a standard chemotherapy regimen as the combination of both of them has been shown overall survival rate of 3.6 months as compared to gemcitabine alone.¹⁷ Patients are usually diagnosed at older age and further it is made worse by symptoms such as pruritus, jaundice, ascites, etc.¹⁸ There has been limited information on the application of autoantibodies (AABs) as biomarkers in case of primary liver tumors such as CCA so far.¹⁹ However, carbohydrate antigen 19-9 (CA19-9) and carcinoembryonic antigen (CEA) were the most commonly studied biomarkers.¹⁹

B.2. Statement of the problem/ rationale/ need of the study:

Studies have shown that the death rate from Cancer is increasing globally, especially in low and middle income countries.^{19,20} Incidence of CCA is increasing in western countries during the last decades and increasing tremendously in Asian countries as well.^{10,19,20} The number of CCA raised from 1720 in 2010 to 2161 in 2013 in England.²¹ The highest incidence of CCA has been reported in northeast Thailand.²²

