Nepal being an Asian country is also in the region to have increased cases of cholangiocarcinoma and need rigorous scientific studies to generate evidence to prepare interventions on its prevention and treatment. Cholangiocarcinoma being the major contributing factor for the death of the humans, this needs early diagnosis and treatment system to intrude the increasing mortality and morbidities. Studies should be conducted in its risk factors, disease status, occurrence and other factors so that such studies are considered to estimate the prevention and management of such deadly diseases.

The studies on this sector is in dearth and is in great need of the involvement of academia, medical centers and different institutions. Such studies will provide evidence to plan several interventions for its better and efficient prevention and treatment option.

B.3. Research hypothesis (if applicable):

NA

B.4. Objectives of the research:

General objective (s)

The aim of the study is to assess the clinico-demographic profile of the patient with cholangio-carcinoma undergoing ERCP in Dhulikhel Hospital.

Specific objective(s):

This study holds the objective,

- To identify clinical profile of the patient with cholangio-carcinoma undergoing ERCP
- To describe the demographic profile of the patient with cholangio-carcinoma undergoing ERCP
- To measure the outcome of ERCP procedure in them.
- To identify the association between demographic variable and clinical presentation of the patient with cholangio-carcinoma undergoing ERCP

B.5. Study site and justification:

The study will be conducted in the Endoscopy unit of the Internal medicine department of Dhulikhel Hospital. This hospital has provided services to more than 50 out of 75 districts of the country. It provides services to about 2.7 million people from Kavrepalanchowk, Sindhupalchowk, Dolakha, Lalitpur, Kathmandu, Sindhuli, Ramechhap and other surrounding districts per-year. In Nepal ERCP procedure has been limited to very few Tertiary centers and Dhulikhel Hospital is the pioneer institute to provide the ERCP procedure (since 2011) in the nation. This procedure is mainly performed for the indication of choledocolithiasis, obstructive Jaundice, acute biliary pancreatitis, cholangiocarcinoma, etc. In 2019 only, a total of 1352 patients had undergone ERCP in Dhulikhel Hospital as per the monthly ERCP report book obtained from the Department of Endoscopy of Dhulikhel Hospital.

B6. METHODS/ METHODOLOGY:

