 - Part I: Socio-Demographic information of patient
 - Part II: Information related to Clinical profile of patient
 - Part III: outcome of ERCP procedure
- The data will then be entered into Microsoft Excel for further data management.

B.8.2. Pretesting

The proforma will be pretested entering about 10 cases so that we can further modify the proforma.

B.8.3. Validity and Reliability of tool

The tool will be the proforma and this will be based on other literatures and as per the experts suggestion. Indeed, the principal investigator is the physician (expert) to perform this procedure in Nepal and other team members have some kind of exposure in this sector.

B.9. Plan for specimen/data management:

(a) Data Processing

- Collected data will be stored in a file to prevent loss or damage.
- Data will be coded and entered in Microsoft Excel Sheet and will be transferred to the Statistical Program for Social Science (SPSS) for further analysis.

(b) Presentation of Data

- Data will be categorized on the basis of research objectives.
- The study will present the descriptive statistics and other details of the variables.

B.10. Plan for data analysis:

B.10. a. SPSS (Statistical Program for Social Science) version 25.0 will be used for descriptive as well as inferential statistics.

B.10. b. Statistical tests: Descriptive statistics (mean, frequency, standard deviation and percentage) will be applied. For inferential statistics, Chi-square test will be used for the analysis of the categorical data while, t-test or correlation will be done for the continuous variables.

B.11. Potential Biases:

There may be some confounders that will direct to the bias of the study. The information in the confounders will be collected and if required will be adjusted in the data analysis.

B.12. Limitations of the study:

- This is not a common disease, so the sample size of the eligible participants is limited.
- The retrospective study nature of this study may not allow us to incorporate as much information as we are seeking. However, future research may address these issues.

B.13. Plan for supervision and monitoring:

- Data will be collected by the co-authors
- Supervision and monitoring will be done by Principal Investigator and the research team

B.14. Plan for dissemination of the research:

The research will be disseminated to:

- Conferences
- Publication in one of the index peer review journal

B.15. DATA AND SPECIMEN BANKING AND/OR SHARING

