5. EUS FNA

- a) Yes
- b) No

6. If Yes

- 1) Positive
- 2) Negative

7. Brush cytology

- a) Yes
- b) No

8. If Yes

- 1) Positive
- 2) Negative

9. Intra ductal biopsy

a) Yes

b) No

10. If Yes

- 1) Positive
- 2) Negative

11. Surgical operability

- a. Operable
- b. Non-operable
- c. Unknown

12. Lab reports

- a) Total bilirubin.....
- b) Direct bilirubin.....
- c) ALP.....
- d) GGT.....
- e) AST.....
- f) ALT.....
- g) PT.....
- h) INR.....

13. Type of growth

- a. Distal
- b. Hilar

1) Bismuth-I

2) Bismuth-II

3) Bismuth-III

4) Bismuth-IV

5) Bismuth-V

Part 3. Outcome of ERCP procedure

14. Type of stent used in ERCP:

- a) Plastic stent
- b) Metal stent (SEMS)

15. Outcome of Stenting

- a) Immediate
- b) Failed Stenting
- c) Successful stenting

16. Complications

- a) Perforation
- b) Bleeding
- c) PEP
- d) PEC

17. If PEP done

- 1) Within 2 weeks
- 2) After 2 weeks

18. If PEC done

- 1) Within 2 weeks
- 2) After 2 weeks

19. Restenting

- a) Yes
- b) No
- 1) Within 1 month
- 2) Within 2 month
- 3) Within 3 month

20. Radio- Frequency Ablation

- Yes
- No

21. Survival Rate

- a) < 1 month
- b) 3-6 month
- c) 6 month- 1 year
- d) >1 year

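### Restenting (item 19) has no category for death or loss before restenting, and item 21 skips 1 to 3 months, so a No cannot be interpreted as stent durability

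*Combined protocol and SAP*

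**What the plan says.** One specific objective in section B.4 is "To measure the outcome of ERCP procedure in them". The data for it come from Part 3 of the proforma.

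- **Item 19**, "19. Restenting", has the answers Yes and No, followed by three timing bands, the last of which is "3) Within 3 month". It has no option for death before restenting, loss to follow-up or unknown status. Item 11 (surgical operability), on the same form, does have an unknown option.
- **Item 21**, "21. Survival Rate", has four bands: under 1 month, 3 to 6 months, 6 months to 1 year, and over 1 year. No band covers 1 to 3 months. The item does not ask for vital status, a starting point or dates.
- **Section B.10.b** says "Descriptive statistics (mean, frequency, standard deviation and percentage) will be applied" and "Chi-square test will be used for the analysis of the categorical data", with a t-test or correlation for continuous variables. It does not mention time at risk or death as a competing event.
- **Section C2.1** says that current status will be obtained by telephone, and only where that is feasible.

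The background in section B.1 says of cholangiocarcinoma: "Hence it is known as the disease with late diagnosis and fatal outcome". The documents give no early-death rate and no restenting rate.

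**The concern.** Consider two patients. One dies three weeks after stenting with the first stent still in place. The other is alive at three months and has not needed another stent. For both, No is the only true answer that item 19 offers. A third patient, who could not be reached after discharge, may also be entered as No, or the item may be left blank. These are different outcomes, and the form gives the analyst no means of telling them apart.

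Deaths inside the restenting window are plausible on the protocol's own account: the disease is described as fatal, and the first survival band is under one month. Item 19 is also the item in Part 3 that records most directly whether the first stent had to be followed by another. A reader of the results may therefore take a low restenting percentage as evidence that stents lasted, when part of it reflects patients who did not live long enough to be restented.

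**Working it through.** **Plan's own figure.** There is none to reproduce. The documents state no restenting rate, early-death rate, denominator or patency endpoint.

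**Can the existing form separate the groups?** Cross item 19 with item 21 for a patient entered as No:

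| Survival of the patient | Band in item 21 | Status in the 3-month window |
|---|---|---|
| Died before 1 month | under 1 month | Partly identifiable; vital status is not asked |
| Died between 1 and 3 months | none | Not identifiable |
| Alive past 3 months | 3 to 6 months or later | Identifiable |
| Not reached | none | Not identifiable; blank or guessed |

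The missing band covers two of the three months in the restenting window, so cross-tabulating the two items as they stand is only a partial remedy.

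**How much could it matter?** This is an illustration; every rate in it is assumed. Let r be the 3-month restenting risk if nobody died, and D the share of all patients who die unrestented within 3 months. Take constant hazards over the window, acting independently, with time measured in units of 3 months.

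- Restenting hazard: a = −ln(1 − r). With r = 0.30, a = 0.3567.
- Death hazard b solves b/(a + b) × [1 − exp(−(a + b))] = D.
- Crude share restented: C = a/(a + b) × [1 − exp(−(a + b))], which equals [1 − exp(−(a + b))] − D.
- Share with unrestented deaths removed from the denominator: C/(1 − D).

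| | D = 0.10 | D = 0.40 |
|---|---|---|
| b | 0.1261 | 0.6290 |
| 1 − exp(−(a + b)) | 0.3829 | 0.6268 |
| Crude share C | 28.3% | 22.7% |
| Not restented, 1 − C | 71.7% | 77.3% |
| Deaths as share of those not restented, D/(1 − C) | 13.9% | 51.7% |
| Unrestented deaths dropped, C/(1 − D) | 31.4% | 37.8% |

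The restenting hazard is the same in both columns, yet the crude share differs by 28.3 − 22.7 = 5.6 points. Dropping the unrestented deaths does not cure this: it gives 31.4% and 37.8% against an assumed 30% in both, a difference of 6.4 points in the opposite direction.

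**Sensitivity.** Now let d be the 3-month death risk if nobody were restented, so that b = −ln(1 − d), and take r = 20%. The crude share is 19.5% at d = 5% and 14.6% at d = 50%, a shortfall of 0.5 to 5.4 points. Dropping the unrestented deaths gives 20.4% and 26.8%.

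**Scale.** Take the stated sample size of 375 (section B.7.5), r = 20% and d = 30%. About 64 patients would be restented, 101 would die unrestented and 210 would be alive without restenting (64 + 101 + 210 = 375). If all the deaths were entered as No, they would make up 101/311 = 32% of that group.

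**The case against.** The strongest reply is that nothing is biased. With complete follow-up, the number restented divided by all patients correctly estimates the share actually restented, with death as a competing event. That is a reasonable quantity for a descriptive chart review whose hypothesis section (B.3) reads not applicable. This stands. The percentage is low only as an estimate of stent failure among patients still at risk, and the plan does not say that it will estimate that.

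Several stronger readings are tempting, and the documents do not support them:

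- *The plan codes early deaths as No.* No coding instruction exists. No is the natural entry, but a blank is equally possible and would change the denominator instead.
- *The plan counts those deaths as stents that lasted.* No section says that No means a lasting stent, and no durability or patency endpoint is defined.
- *Restenting is assessed at 1, 2 and 3 months.* The bands read more naturally as the timing of a Yes, in the manner of items 17 and 18. The form then sets no horizon for a No. The 3-month horizon used above is simply the longest band.
- *Comparisons between sicker and fitter groups will be distorted.* The only association objective in section B.4 links demographic variables with clinical presentation. No comparison of restenting by operability or stent type is planned.
- *The distortion is 9 points.* A reader might take 0.30 × 0.90 = 27% and 0.30 × 0.60 = 18%. That fixes at 30% the proportion restented among patients who did not die unrestented, a group selected by outcome. It does not represent equal stent durability; with equal restenting hazards the gap is 5.6 points.

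What survives is narrower. The form cannot distinguish the outcomes, and the plan does not say which quantity the percentage stands for.

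**Conclusion.** The point holds as a gap in the data collection form, and it is a cheap improvement rather than a flaw that undermines the study. Items 19 and 21 together cannot separate patients alive without restenting from those who died unrestented or were lost. A crude percentage is acceptable if it is labelled as the share of patients actually restented and follow-up is complete. It should not be read as stent durability under the third specific objective, because in that reading it understates stent failure among patients at risk.

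The direction of that understatement follows from the structure of the item, provided that deaths are entered as No. Its size cannot be derived from the documents. The illustrations put it between half a point and about 7 points (30 − 22.7 = 7.3), assuming constant independent hazards, restenting risks of 20% or 30%, and the early-death levels shown. If few patients die within three months, it is negligible.

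**What to change.** Make the change at the pretest of about 10 cases already planned in section B.8.2:

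1. Add died without restenting and status unknown to item 19, and state how each is to be entered.
2. Close the 1 to 3 month gap in item 21. Alternatively, record the dates of stenting, restenting, death and last contact, which serves both items.
3. In section B.10.b, state that status at 1 and at 3 months after stenting will be reported as three proportions: restented, alive without restenting, and died without restenting. Show status unknown as a separate count and state the denominator. Where status is complete, these proportions are already the competing-risk estimates and need no modelling.
4. Do not report a durability rate that leaves out patients who died unrestented, because it errs upward.

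The cost is a small revision of the form, a little more abstraction work per record, and a line or two of analysis text. It is more than a cross-tabulation of existing items, since item 21 has to change. The downside is that some patients will move to status unknown, because telephone follow-up reaches only feasible cases (section C2.1). That would show a gap in the data that the present form hides.

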B.6.1 Research Methods (Cross in the appropriate box)

a) Qualitative Research Quantitative Research c) Mixed Research

B.6.2. Study design:

This is a quantitative, retrospective, descriptive cross-sectional observational study.. The outcome and the exposure will be measured at the same time as a snapshot.

B.6.3. Study Variables

The study variables will be the socio-demographic variables and the clinical details of the study participants.

B.6.4. Expected outcomes of the research

The expected outcome of the research is to present a clinical finding of this under studied clinical area in Nepal. Furthermore, this will be a reference for the future researchers to conduct further studies on this sector to enhance the prevention, management and the treatment services.

B.7 STUDY POPULATION AND SAMPLE

B.7.1. Participants/ study population:

Patients with cholangiocarcinoma who had undergone ERCP in Endoscopic Department of Dhulikhel Hospital. The patient's information will be obtained from patients' medical records from the outpatient and inpatient department of Dhulikhel Hospital. Thus, the person will not be contacted directly for the data collection.

B.7.2 Selection criteria:

Inclusion criteria:

- All the participants with cholangiocarcinoma had undergone ERCP
- above 18 years of age.

Exclusion criteria:

- ERCP failed cases

B.7.3. Sampling method/ technique:

We will do purposive sampling from the eligible list obtained from the medical records.

B.7.4. Sampling Unit:

The sampling unit is the patient with cholangiocarcinoma who had undergone ERCP.

B.7.5 Sample size determination:

All the eligible cases listed in the medical record of Dhulikhel Hospital from January 2017 to January 2023. Hospital records showed approximately 75 cases of cholangiocarcinoma per year. So, we will conduct a total population sampling with an estimated sample size of 375.

B.8. Procedure:

First of all, the researcher will get formal approval for data collection in the institution.

- After ethical clearance, data will be collected through a case sheet of the patient and record of ERCP procedure at the department using prepared Per forma.
- Data of procedure outcome will be collected via call to the patient. Before collecting information from the respondent, they will be informed about the objective of the study and will be assured of privacy and volunteering participation.

B.8.1. Data Collection Tools/ Measures:

- Clinical Proforma will be used to collect data

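### The three restenting time boxes in proforma item 19 overlap and carry no tick rule or date, so the same early restent can be coded in different ways

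*Combined protocol and SAP*

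**What the plan says.** Item 19 of the proforma (Part 3, outcome of ERCP) asks Yes or No for restenting and then offers "1) Within 1 month", "2) Within 2 month" and "3) Within 3 month". There is no field for the date of the ERCP or of the restent, no later time category, and no instruction on how many boxes to tick. The form's only direction is a general request for correct answers.

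Items 17 and 18, just above, split time into two exclusive boxes, the second being "2) After 2 weeks".

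Item 19 serves the third specific objective in B.4: "To measure the outcome of ERCP procedure in them". For analysis, B.10.b says "Descriptive statistics (mean, frequency, standard deviation and percentage) will be applied" and adds generic tests, with no rule for this item. B.13 assigns data collection to the co-authors, so more than one person will complete the form.

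**The concern.** The labels are cumulative in wording but are numbered like alternative codes. An abstractor who follows the form literally has three correct answers for a first-month restent and two for a second-month one. Which box or boxes are ticked then depends on the abstractor's habit, and the meaning of each row in the frequency table depends on it too.

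At stake is the timing of restenting, one of four timed items in Part 3 (17, 18, 19 and 21). A row published under a cumulative label but holding only one month's restents would mislead a reader. A row that mixes the two conventions has no clear meaning.

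**Working it through.** **Step 1: how many boxes does a restent satisfy?** Read literally, the boxes are the intervals (0,1], (0,2] and (0,3] months, each inside the next. Taking a month as about 30 days:

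| Restent on | Box 1 true | Box 2 true | Box 3 true | Number true |
|---|---|---|---|---|
| day 20 | yes | yes | yes | 3 |
| day 45 | no | yes | yes | 2 |
| day 80 | no | no | yes | 1 |

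A restent after three months satisfies none. It can be recorded only as Yes with no time.

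**Step 2: what would the rows show under each ticking practice?** Let a, b and c be the numbers restented in the first, second and third month. The labels, read literally, mean a, a+b and a+b+c.

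- Every true box ticked: rows are a, a+b, a+b+c. The labels are correct.
- Only the narrowest true box ticked: rows are a, b, c. Row 2 omits a and row 3 omits a+b.
- One tick in any true box: row 1 can be anything from 0 to a, row 2 from 0 to a+b, and row 3 from c to a+b+c.

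**Step 3: illustration.** The documents give no restenting figure to reproduce. The counts below are assumptions. The denominator is the 375 from B.7.5 ("total population sampling with an estimated sample size of 375"), used here only as a scale.

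| Assumed a, b, c | Narrowest-box rows, % of 375 | Literal meaning of labels, % of 375 | Row 2 shortfall, a/375 | Row 3 shortfall, (a+b)/375 |
|---|---|---|---|---|
| 10, 10, 10 | 2.7, 2.7, 2.7 | 2.7, 5.3, 8.0 | 2.7 points | 5.3 points |
| 20, 30, 40 | 5.3, 8.0, 10.7 | 5.3, 13.3, 24.0 | 5.3 points | 13.3 points |
| 40, 30, 20 | 10.7, 8.0, 5.3 | 10.7, 18.7, 24.0 | 10.7 points | 18.7 points |
| 60, 30, 10 | 16.0, 8.0, 2.7 | 16.0, 24.0, 26.7 | 16.0 points | 24.0 points |

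Over these four splits, row 2 leaves out a/(a+b) = 40% to 67% of the restents its label covers, and row 3 leaves out (a+b)/(a+b+c) = 56% to 90%.

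For the 20, 30, 40 split (90 restents), ticking every true box gives rows of 20, 50 and 90, which is 160 ticks. One tick in any true box could give 0 to 20, 0 to 50 and 40 to 90.

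**Step 4: can it be undone?** If everyone ticks the narrowest box, summing the rows gives a, a+b and a+b+c exactly. If everyone ticks all true boxes, subtracting successive rows gives a, b and c. If single-tick practice is mixed, neither operation works, and the timing has to be read again from the source.

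**The case against.** The strongest reply is that the harm depends on behaviour that the documents do not describe. An understatement needs one tick per patient in the narrowest box, and nothing in the form requires that. Symptoms, Investigations and Complications are plausibly items where several boxes may be ticked. If item 19 is handled in that way, its rows are correct as labelled. If it is instead handled like items 17 and 18, the codes would be read as successive months, and summing recovers the cumulative figures. Either consistent practice loses nothing. This stands, and it limits the point to ambiguity and possible mislabelling.

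Two stronger readings are tempting, and the documents support neither.

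- A reader might infer that the reported percentages will be badly understated. With an assumed 40, 30 and 30 among 100 patients restented within three months, the narrowest-box rows fall 40 and 70 points short of their labels. That split is invented, and the denominator holds only patients restented by three months, so the last figure is 100% by construction. It also presupposes the narrowest-box rule.
- A reader might infer that the data could never be repaired because no date is recorded. B.8 draws on the patient's case sheet and the department's ERCP record, so timing taken from those sources can be read again. Only restents known solely from the telephone call would be harder to recover.

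What the reply does not answer is mixed practice. Several co-authors abstract, and no rule in the documents makes them tick alike.

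**Conclusion.** The point holds as an ambiguity in one descriptive outcome item. The overlap follows from the labels alone, and no tick rule, coding rule or date field elsewhere resolves it. Whether the reported timing would be wrong depends on abstractor practice: correct if every true box is ticked, mislabelled but recoverable by summing if the narrowest box is always ticked, and uninterpretable without the source records if practice is mixed.

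The size of any error cannot be stated, since the documents give no restenting rate. The shortfalls tabulated above rest on assumed counts and on narrowest-box ticking. The proportion restented at all, from the Yes/No part, is untouched, and B.3 states no hypothesis that could be affected. The weight is low. The reason to act is that the correction costs almost nothing now, whereas mixed coding would mean reading records again later.

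**What to change.** Before abstraction starts, change item 19 as follows.

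- Relabel the three existing boxes as exclusive intervals: up to 1 month; more than 1 to 2 months; more than 2 to 3 months.
- Add a fourth box for more than 3 months, so that every Yes has a time category.
- Print an instruction to tick one box per patient, for the first restent.
- In B.10, state that any cumulative figure at k months is the sum of the boxes up to k.

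The cost is three labels, one added box and two sentences. B.8.2 already makes room for it: "The proforma will be pretested entering about 10 cases so that we can further modify the proforma". Exclusive boxes lose nothing that the present labels were meant to capture.

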B15.1 Management of specimen/data archiving or left-over

NA

B15.2 Specimen/data sharing plan

NA

C. ETHICAL CONSIDERATION

10.1. Ethical issues	Yes/ No	Justification if yes
a. Are human participants included in the study?	Yes	The study aims to determine the clinico-demographic profile of the patients with cholangiocarcinoma undergoing ERCP in Dhulikhel Hospital. But we will not have face to face interaction, as all the information will be obtained from the medical records.
b. Are vulnerable members of the population required for this research? (includes age under 18, pregnant women etc)	No	
c. Are there any risks involved for the participants? If yes, identify clearly what are the expected risks for the human participants in the research and provide a justification for these risks.	No	
d. Are there any benefits involved for the participants? If yes, identify clearly what are the expected benefits for the participants.	No	

C1. SIGNIFICANCE OF THE STUDY

- The study can reveal some risk factors associated with the particular disease i.e Cholangiocarcinoma. Thus, it can be regarded as a baseline study for conducting any intervention.
- It can also be used as a reference for future study purposes in similar types of study.

C2. BALANCE OF RISK AND BENEFIT

C2.1 Risk of the study and Preventive and alleviative measures for risk

C2.1. Risk management:	
Potential risks identified	Proposed measures to mitigate risks
1. No direct risk/harm to the study participants as medical records will be reviewed primarily for patient data collection.	NA
2. Information on the patient's current status will be gathered via telephone interview (only for the feasible cases) where they may have to spare a few minutes for the data, however, this will take only a few minutes.	Verbal consent will be taken and all the information will be provided to the participants if the interaction is required.

C2.3 Benefits of the study

The study will be helpful to the future researcher to base on this and plan further studies so that we can enhance the prevention and treatment processes.

C3. CONSIDERATION FOR VULNERABLE RESEARCH PARTICIPANTS

Check whether your study involves any of the following vulnerable research participants.

- Prisoners
- Pregnant women
- Mentally ill persons
- Cancer or terminally ill patients
- Neonates/infants/children (aged <18)
- HIV/AIDS patients
- Institutionalized persons e.g. military, students, etc.
- Others (please specify).....

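### Proforma item 19 has no place to record a restent after three months, so late restents may be left untimed, put in the wrong box or counted as none

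*Combined protocol and SAP*

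**What the plan says.** Proforma Part 3 covers the outcome of ERCP. Item 19 records restenting as Yes or No and lists three time boxes, for one, two and three months; the last reads "3) Within 3 month". Item 20 follows directly. The item has no later box, no not-recorded box, no date field and no instruction on which box to tick.

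Other timed items in Part 3 end differently. Items 17 and 18 close with "2) After 2 weeks", and item 21 (survival) has a last category for more than one year.

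The item serves the third specific objective in B.4, "To measure the outcome of ERCP procedure in them". B.9(b) adds that "The study will present the descriptive statistics and other details of the variables".

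On sources, the first bullet of B.8 takes data from case sheets and the department's ERCP records. The second says "Data of procedure outcome will be collected via call to the patient". C2.1 describes the patient's current status as being "gathered via telephone interview (only for the feasible cases". B.12 accepts that a retrospective study may not yield all the information wanted.

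On changes to the form, B.8.2 says "The proforma will be pretested entering about 10 cases so that we can further modify the proforma".

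**The concern.** An abstractor who finds a restent at, say, five months has no correct box. Nothing in the protocol says what to do then, so different abstractors may do different things, and the completed form will not show which choice was made.

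Two results are at stake. One is the table of restenting time, which could not say how many restents were late and how many untimed. The other is the simple restenting rate, which would be too low if some late restents were ticked No. Both are descriptive results under the third specific objective. Putting them right after data entry would mean reopening charts from the January 2017 to January 2023 window.

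**Working it through.** There is no plan figure to reproduce, so the check sets the possible true events against the entries that item 19 allows. Boxes 1, 2 and 3 are the one-, two- and three-month boxes.

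| True event | Entries the form allows or invites |
|---|---|
| Up to 1 month | Yes + {1} or {1,2,3}; also {2}, {3} or {2,3} if only later boxes are ticked |
| More than 1 to 2 months | Yes + {2} or {2,3}; also {3} alone |
| More than 2 to 3 months | Yes + {3} |
| More than 3 months | Yes + no box; or Yes + {3} as the nearest box; or No, if the item is read as restenting within three months |
| Restented, time unknown | Yes + no box |
| Not restented | No |

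Reading the table backwards:

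- **Yes with no box** is either a late restent or one of unknown timing.
- **Yes with box 3 alone** is a restent at more than 2 to 3 months, an earlier one marked only in a later box, or a late one forced in.
- **No** is either no restent or a late restent.

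In symbols, let L1, L2 and L3 be the late restents entered as Yes with no box, as box 3, and as No. Let U be the restents of unknown timing, R all restents and n the patients in the denominator.

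- True number of late restents: L = L1 + L2 + L3.
- Untimed Yes records: b = L1 + U.
- Recorded restenting rate: (R − L3)/n, which is too low by L3/n.
- Box 3 is inflated by L2.

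The documents give none of R, L1, L2, L3 or U, so neither the shortfall nor the misclassification can be estimated. For scale only, B.7.5 says "So, we will conduct a total population sampling with an estimated sample size of 375". If all 375 were stented, each late restent ticked No would lower the rate by 1/375 = 0.27 percentage points. The step is larger if fewer were stented, which is possible because item 15 has a failed-stenting category.

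**Overlap.** A restent within one month is also within two and within three. If abstractors tick the earliest box, or every box that applies, the lowest tick recovers the band for any timed restent up to three months. It fails when only a later box is ticked, and when a late restent has been put in box 3.

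**The case against.** **A three-month window may have been intended.** No section says so, and item 21 follows survival past one year, so late restents can fall within the time the form covers. Even with such a window, the abstractor would need to know whether a later restent is a No or a Yes with the time left blank.

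**The pretest may catch it.** B.8.2 exists to allow changes to the form, and that stands as a route to repair. It commits to no change in item 19, though, and about 10 cases may include no late restent. If the late-restent share were 2%, 5% or 10% (assumed values), 10 independent cases would contain none with probability 0.98^10 = 82%, 0.95^10 = 60% or 0.90^10 = 35%.

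**Most items on the form lack a not-recorded box.** This is true of smoking, comorbidity and items 14, 16, 20 and 21, for example. The unknown option in item 11 may mean that operability was undetermined rather than that data were missing. This objection stands: the lack of a not-recorded box is the general style of the form. The weakness particular to item 19 is the missing late category, judged against items 17, 18 and 21.

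**Unknown timing.** A reader might infer from the telephone follow-up that unknown timing is likely. The documents do not show that. B.8 first names case sheets and ERCP records, and C2.1 ties the feasible-case calls to current status. Given B.12, unknown timing is possible, and no more can be said.

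**Conclusion.** The point holds as a minor weakness in one descriptive outcome item. As printed, item 19 cannot correctly record the time of a restent after three months, and nothing tells the abstractor how to enter one. The restenting-time description may be incomplete or misclassified, and the Yes/No rate may be too low. The size is unknown because the documents give no restenting rate. No hypothesis, planned test or sample-size figure names restenting time.

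Two stronger readings are tempting, and the documents support neither.

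- A reader might infer that the number of late restents lies between zero and the count of untimed Yes records (b). That requires L2 + L3 = 0, and no coding rule ensures it. Even b = 0 would not show that there were no late restents.
- A reader might infer that the overall Yes/No rate is safe whatever happens to the timing. That holds only if every late restent is ticked Yes, which the form does not say.

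The verdict assumes that the time boxes apply to patients ticked Yes, and that no separate abstraction instruction exists outside the documents.

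**What to change.** Before abstraction begins, for example at the B.8.2 pretest:

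1. Replace the three boxes with exclusive bands: up to 1 month, more than 1 to 2 months, more than 2 to 3 months, more than 3 months, and not recorded. Alternatively, record the date of first restenting from the ERCP record where it is available, and derive the bands from it. Only the date shows when a late restent took place.
2. State on the form that Yes covers restenting at any time after the index procedure.
3. Report each band, including not recorded, as a percentage of stented patients.

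The cost is one form edit. Some dates will still be missing and will stay in the not-recorded band, and restents done at other hospitals may still be missed.
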